2.13 Follow-up Procedures.....	15
2.13.1 Four-Week Post-Final Treatment Visit; 4 Weeks \pm 1 week;.....	15
2.13.2 Twelve-Week Post Final Treatment Visit; 12 Weeks \pm 2 weeks.....	15
2.13.3 Optional Follow-Up Evaluations (up to 4 within study period).....	15
2.14 Assessments	17
2.14.1 Global Aesthetic Improvement Scale (GAIS-Subject).....	17
2.14.2 Body Satisfaction Questionnaire – Abdomen.....	17
2.14.3 Body Satisfaction Questionnaire – Buttocks	17
2.14.4 Photography	17
2.14.5 [REDACTED]	18
2.14.6 [REDACTED]	18
2.14.7 Photograph Review	18

ZELTIQ P/N: [REDACTED]
Protocol Number: ZA19-002

This document and the contents hereof are considered proprietary and confidential information of ZELTIQ Aesthetics, Inc. Disclosure to unauthorized individuals or dissemination, publication or copying is prohibited without prior written consent of ZELTIQ.

2.15 Endpoints.....	18
2.15.1 Primary Endpoints	18
2.15.2 Secondary Endpoints	19
2.16 Statistical Analysis Plan	19
2.16.1 Statistical Methods: Overall Plan.....	19
2.16.2 Analysis Population	19
2.16.3 Endpoint Analysis	19
Primary Endpoints:.....	19
Secondary Endpoint:	20
2.17 Protocol Adherence	20
2.18 Adverse Events	20
3. Study Management and Quality Control.....	23
3.1 Study Data Collection	23
3.2 Confidentiality	23
3.3 Investigator Responsibilities	24
General Responsibilities.....	24
Investigator Records.....	24
Investigator Reports	25
3.4 Sponsor Responsibilities	26
General Responsibilities:.....	26
Training	27
Site Monitoring.....	27
Final Report	28
4. Data Ownership	28
5. Publication Policy.....	29
6. Risk/Benefit Analysis	29
6.1 Benefits	29
6.2 Risks.....	29
7. Selected References	31

Protocol Summary

Title	Electromagnetic Muscle Stimulation for Abdominal and Gluteal Muscle Toning
Design	Prospective, multi-center, non-randomized, interventional
Purpose	Evaluate the use of Electromagnetic Muscle Stimulation for body contouring
Enrollment	Up to 200 subjects
Clinical site(s)	Up to 20 investigational sites
Subject Population	Healthy adult men and women aged 22 – 65 who desire abdominal and/or gluteal muscle toning.
Primary Endpoints	Efficacy endpoint: Measurement of subject feeling about body shape, assessed using the Body Satisfaction Scale at the 4-Week follow-up visit.
Secondary Endpoint	Safety endpoint: The frequency of device-related adverse events (AEs) including device-related serious adverse events (SAEs) will be summarized. Secondary endpoint: Subject-graded improvement in the treated area using the Subject Global Aesthetic Scale (SGAIS) at the 4-Week follow-up visit.
Sponsor	ZELTIQ Aesthetics, an Allergan affiliate [name] [name], CA 94588

ZELTIQ P/N: [REDACTED]
Protocol Number: ZA19-002

This document and the contents hereof are considered proprietary and confidential information of ZELTIQ Aesthetics, Inc. Disclosure to unauthorized individuals or dissemination, publication or copying is prohibited without prior written consent of ZELTIQ.

1. Introduction

1.1 *Background*

Fat reduction and body contouring procedures, which include invasive, minimally-invasive, and non-invasive procedures, have become increasingly popular aesthetic procedures.

Patients who are obese and do not have specific fat bulges but require significant fat reduction to achieve aesthetic results are candidates for invasive and minimally-invasive procedures, such as liposuction and laser-assisted liposuction. Although effective at reducing fat, these invasive and minimally-invasive procedures involve significant patient discomfort, expense, downtime, and the risks typically associated with surgical procedures. As a result, patients who do not require significant fat reduction to achieve meaningful aesthetic results typically seek non-invasive fat reduction and body contouring procedures to avoid the pain, expense, downtime, and surgical risks associated with invasive and minimally-invasive procedures.

ZELTIQ Aesthetics has developed and commercialized a technology for cold-assisted lipolysis. The ZELTIQ CoolSculpting technology is based on the sensitivity of fat cells to cold injury in order to selectively eliminate subcutaneous fat tissue without affecting the skin or other surrounding tissues. The technology, cryolipolysis, enables a non-invasive alternative for subcutaneous fat reduction through cellular apoptosis. The ZELTIQ CoolSculpting System is cleared for use in the United States for the indication of cold-assisted lipolysis of various body areas, including the abdomen, flanks, thighs, submental and submandibular areas, back fat, bra fat, and banana roll. It has been clinically proven to reduce fat bulges, allowing patients to achieve noticeable and measurable aesthetic results without the pain, expense, downtime, and risks associated with existing invasive and minimally-invasive procedures.

While the CoolSculpting procedure is successful in reducing subcutaneous fat in the abdomen, ZELTIQ Aesthetics is exploring the concept of combining other non-invasive aesthetic treatment modalities to enhance and/or improve the contouring effects of CoolSculpting.

One treatment of interest is the use of electromagnetic muscle stimulation (EMS) [REDACTED]

[REDACTED] Electromagnetic muscle stimulation (EMS), also known as neuromuscular electrical stimulation (NMES) is the elicitation of muscle contraction using

ZELTIQ P/N: [REDACTED]
Protocol Number: ZA19-002

This document and the contents hereof are considered proprietary and confidential information of ZELTIQ Aesthetics, Inc. Disclosure to unauthorized individuals or dissemination, publication or copying is prohibited without prior written consent of ZELTIQ.

electric impulses. The impulses mimic the action potential that comes from the central nervous system, causing the muscles to contract.^[1]

EMS devices are frequently used in physical therapy or rehabilitation settings to strengthen and tone muscles damaged by illness or disease but they may also be used for other purposes.^[2] High intensity EMS devices can elicit stronger, more effective muscle contractions believed to increase muscle strength and endurance. EMS has received an increasing amount of attention in the last few years from fitness enthusiasts as various manufacturers promote the technology for muscle strengthening, firming and improvement in muscle tone specifically in the abdomen, buttocks and thighs.^[3]

1.2 Device Descriptions

EMS Devices

Electromagnetic (EMS) devices that may be used in this evaluation produce electromagnetic muscle stimulation by a non-contact magnetic field in tissue. Each device under consideration for use in this study has the same indications for use and similar technological characteristics and principles of operation. Figure 1 below depicts a representative EMS device.

[figure not shown]

Figure 1. Representative EMS Device

This study will evaluate the feasibility of EMS treatments for improvement in abdominal and buttock contouring. [REDACTED]

[REDACTED] One or more EMS devices may be used in this evaluation.

The EMS devices considered for use in the proposed evaluation have the following indications:

- Improvement of abdominal tone, strengthening of the abdominal muscles, development of firmer abdomen.
- Strengthening, toning and firming of buttocks

EMS devices utilized in this study will be operated in accordance with the manufacturer's Instructions for Use.

The materials used for patient-contacting surfaces are all common materials with a history of use in medical and/or skin-contact consumer applications or have been tested for biocompatibility.

1.3 Regulatory Status

The EMS devices that may be used in the proposed evaluation are non-significant risk devices. [REDACTED]

[REDACTED]
[REDACTED]
[REDACTED]

2. Study Protocol

2.1 Design

Prospective, multi-center, non-randomized, interventional study

2.2 Study Duration

Enrollment and follow-up are expected to take up to four (4) months for each subject.

2.3 Physician Participants

Study Investigators must be practicing medical physicians with experience in the use of the CoolSculpting System.

2.4 Site Requirements

Site Investigators should have at least one study coordinator with experience in conducting aesthetic research and with sufficient time to perform study activities.

2.5 Subject Recruitment

Patients who seek abdominal and/or gluteal muscle firming and toning will be recruited for this study.

2.6 Sample Size

A maximum of 200 subjects will be included in the study.

2.7 Subject Eligibility

To be eligible to participate, subjects must meet all of the inclusion criteria and none of the exclusion criteria listed in **Table 1**.

Table 1. Eligibility criteria.

Inclusion Criteria

- a) Male or female ≥ 22 years and ≤ 65 years of age.
- b) Subject has not had weight change exceeding 5% of body weight in the preceding month.
- c) Subject agrees to maintain body weight within 5% during the study by not making any changes in diet or exercise routine.
- d) Subject has a BMI ≤ 30 as determined at screening.

- e) Subject agrees to have photographs taken of the treatment area(s) during the scheduled time periods.
- f) Subject agrees to refrain from any new abdominal and/or gluteal muscle training exercises of the treatment area during the course of the study.
- g) Subject agrees to avoid sun tanning during the course of the study.
- h) Subject has read and signed the study written informed consent form.

Exclusion Criteria

- a) Subject has had a recent surgical procedure(s) in the area of intended treatment and muscle contractions may disrupt the healing process.
- b) Subject has had an invasive fat reduction procedure (e.g., liposuction, mesotherapy) in the area of intended treatment.
- c) Subject needs to administer or has a known history of subcutaneous injections into the area of intended treatment (e.g., heparin, insulin) within the past month.
- d) Subject has not had an intrauterine contraceptive device inserted or removed within the past month.
- e) Subject has a bleeding disorder
- f) Subject is taking or has taken diet pills or supplements within the past month.
- g) Subject has a metal implant or active implanted device such as a cardiac pacemaker, cochlear implant, intrathecal pump, hearing aids, defibrillator, or drug delivery system.
- h) Subject agrees not to change muscle exercise routine in the treatment area (abdominal and/or gluteal) while participating in the study
- i) Subject has pulmonary insufficiency.
- j) Subject has a cardiac disorder.
- k) Subject has a malignant tumor.
- l) Subject has been diagnosed with a seizure disorder such as epilepsy.
- m) Subject currently has a fever.
- n) Subject is diagnosed with Grave's disease.
- o) Subject is pregnant or intending to become pregnant during the study period (in the next 9 months).
- p) Subject is lactating or has been lactating in the past 6 months.
- q) Subject is unable or unwilling to comply with the study requirements.
- r) Subject is currently enrolled in a clinical study of any other investigational drug or device.
- s) Any other condition or laboratory value that would, in the professional opinion of the Investigator, potentially affect the subject's response or the integrity of the data or would pose an unacceptable risk to the subject.

2.8 ***Informed Consent***

Study candidates shall receive an explanation of the study objectives, possible risks and benefits of the study, and be given adequate time to read the information included in the informed consent document. Candidates will be given an opportunity to ask questions about any of the information contained in the informed consent. Candidates must verbally acknowledge understanding of the informed consent and sign the consent form accordingly. This form must have prior approval of the Institutional Review Board (IRB).

2.9 ***Screening Procedures***

Once informed consent is obtained, interested subjects will undergo screening.

Screening Visit; Required; Day -60 to Day 0

After the informed consent is signed, subjects will be screened to determine if all eligibility criteria are met. The Investigator or designee shall complete a brief medical history and examine the subject to confirm eligibility for the study.

1. Obtain height and weight.
2. Calculate BMI.
3. Assess for any medical conditions that would lead to exclusion of a subject from the study.
4. [REDACTED]
- [REDACTED]
- [REDACTED]
5. Document medication use, Fitzpatrick Skin Type, and ethnicity.
6. All female subjects of childbearing potential will be asked to take a pregnancy test (urine) prior to being treated. If the subject is pregnant, she will be excluded from participation.

Female subjects of childbearing potential will be advised to avoid becoming pregnant during the study by using a medically accepted form of contraception if they are sexually active. If the subject becomes pregnant during the study, she will not be treated subsequently with the study device or be required to have follow-up photographs taken or any other efficacy assessment performed.

All subjects will be asked to maintain their weight by not making any major changes to their diet or exercise regimen during the study. Subjects who do not maintain their weight within 5% will continue in the study. However, if the weight change is more than 5% after the final treatment, the subjects' data will be excluded from the per-protocol data analysis.

ZELTIQ P/N: [REDACTED]
Protocol Number: ZA19-002

Subjects that do not meet all eligibility criteria will be excluded from further participation in the study.

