2.17 Protocol Adherence

The study Investigators are responsible for performing the study in compliance with the protocol. Non-adherence to the protocol is to be classified as a protocol violation or protocol deviation as defined below.

Protocol Violation

Non-adherence to the protocol that may result in significant additional risk to the subject (e.g., enrollment of a subject who does not meet the study criteria). Or, non-adherence to Good Clinical Practices (GCP) that may impact patient safety (e.g., failure to obtain proper consent prior to performing study procedures). Violations should be reported to the study Sponsor within 5 working days and reported to the IRB per IRB guidelines.

Protocol Deviation

Non-adherence to study procedures which does not result in additional risk to the subject (e.g., subject missed visit). Protocol deviations are not required to be reported to the IRB; however, they must be recorded on the study case report forms and may be reported and reviewed in conjunction with the progress report as part of the annual review process.

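### Exclusion criteria (d) and (h) are worded backwards: read literally, no subject can be eligible, and (d) taken alone passes only women with a recent IUD insertion or removal

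*Combined protocol and SAP*

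**What the plan says.** Table 1 in section 2.7 governs eligibility under the rule that "subjects must meet all of the inclusion criteria and none of the exclusion criteria". Five of its items matter here.

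- Inclusion (a): "Male or female ≥ 22 years and ≤ 65 years of age".
- Inclusion (c): "Subject agrees to maintain body weight within 5% during the study by not making any changes in diet or exercise routine".
- Inclusion (f): "Subject agrees to refrain from any new abdominal and/or gluteal muscle training exercises of the treatment area during the course of the study".
- Exclusion (d): "Subject has not had an intrauterine contraceptive device inserted or removed within the past month".
- Exclusion (h): "Subject agrees not to change muscle exercise routine in the treatment area (abdominal and/or gluteal) while participating in the study".

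Section 2.9 excludes from further participation anyone who does not satisfy the full list. Section 2.12 and Table 2 require the list to be confirmed again before each of the four EMS treatments. Section 2.17 gives "enrollment of a subject who does not meet the study criteria" as its example of a protocol violation. Violations go to the sponsor within 5 working days and to the IRB under that board's own guidelines.

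**The concern.** Two items in the exclusion list are phrased as conditions a subject ought to satisfy. Because they sit under exclusions, each turns away the people the rest of the protocol means to enrol. Exclusion (h) turns away those who accept the exercise restriction that inclusions (c) and (f) impose. Exclusion (d) turns away all men, and all women without a recent IUD insertion or removal.

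The list is an operative rule, and several things depend on it.

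- **Sites.** Up to 20 sites must sign eligibility against text that cannot be satisfied, and each has to decide for itself how to read it.
- **Monitors.** Section 3.4 asks them to verify that only eligible subjects are enrolled, which cannot be done against this wording.
- **Violation reporting.** Read literally, every enrolment matches the example in section 2.17.
- **The IUD screen.** An eligibility form copied from Table 1 would not flag a recent IUD insertion or removal as a reason to exclude.

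**Working it through.** The plan states no figure on this point, so the check is one of logic, using the Table 1 wording.

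**Step 1: (c) against (h).** Inclusion (c) requires agreement to make no change in exercise routine. A subject who agrees to that has also agreed to make none in the treated area, which is the condition in exclusion (h). So meeting (c) triggers (h). A subject who declines the undertaking escapes (h) but fails (c), and arguably also meets exclusion (q), "Subject is unable or unwilling to comply with the study requirements". No subject passes both (c) and (h).

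**Step 2: (f) against (h).** This pair alone does not empty the set. A subject could promise no new exercises and still decline to keep the existing routine unchanged. The empty set therefore comes from (c).

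**Step 3: (d) against (a).** Exclusion (d) applies to anyone without an IUD insertion or removal in the last month. That covers 100% of men, whom (a) admits, and every woman without such an event. On its own, (d) passes only women who had one.

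**Step 4: the combinations.** The profiles cover sex, recent IUD insertion or removal, and agreement to each exercise undertaking. Those that satisfy (c), (f), (d) and (h) together are:

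| (d) | (h) | Eligible profiles |
|---|---|---|
| as written | as written | none |
| reversed | as written | none |
| as written | reversed | only women with an IUD inserted or removed in the last month |
| reversed | reversed | men, and women without a recent IUD insertion or removal, who agree to keep their routine |

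**Step 5: sensitivity to (c).** Section 2.9 speaks more softly, of avoiding major changes. Suppose (c) is set aside altogether and (d), (f) and (h) are kept as written. One profile then passes: a woman with a recent IUD insertion or removal who will start no new exercises but does not agree to keep her routine unchanged. The list still fails to describe the intended population.

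**Step 6: size.** The enrolment cap is 200 (section 2.6). The checks per subject are screening plus four treatments, 1 + 4 = 5. The ceiling on confirmations is 200 × 5 = 1,000, reached only if 200 subjects enrol and each attends all four treatments.

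**The case against.** The best reply is that these are slips that any competent site would read by intent. Inclusions (c) and (f) and exclusion (q) all point the same way on exercise, so only one reading of (h) is workable. For (d), the admission of men in (a) and the item's place in an exclusion list suggest its purpose. Exclusion (s) also lets the investigator turn away a subject at unacceptable risk. Much of this is fair, and enrolment would probably not stop.

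Four narrower points also have weight.

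- The result that only women with a recent IUD event pass needs (h) read by intent and (d) read literally. With both read literally, nobody passes.
- Section 2.17 defines a violation by possible significant added risk to the subject. A man who fails (d), or a subject who fails (h) by agreeing to keep the routine, carries no evident added risk, so the classification is arguable despite the section's own example.
- The eligibility form is not in the documents, so how it words these items is unknown.
- The analysis populations in section 2.16.2 rest on treatment, follow-up and weight change. Failing Table 1 does not remove anyone from the analysis.

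None of this repairs the text. Exclusion (s) allows further exclusions at the investigator's discretion, but it cannot waive (d) or (h). It also does not direct exclusion for a recent IUD insertion or removal. No other section corrects either item, and both are complete lettered sentences, so neither redaction nor text extraction explains them.

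**Conclusion.** The concern holds. As written, Table 1 admits 0 of up to 200 subjects, because inclusion (c) and exclusion (h) cannot both be passed. Separately, exclusion (d) removes all men and leaves only women with a recent IUD insertion or removal. The first result assumes that agreeing to no exercise change covers the treated area, which the wording of (c) supports. The second needs no assumption beyond the text.

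The 1,000 unsignable confirmations are a ceiling, not a forecast. The realistic harm is ambiguous eligibility records, uncertain violation classification across sites, and an IUD screen that points the wrong way if its wording is carried onto a form. No effect on the endpoint definitions or on who is analysed follows from this error. It should still be corrected as a must-fix item, because it lies in a rule applied five times per subject.

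**What to change.** 1. Delete exclusion (h), since inclusions (c) and (f) already carry the requirement, or restate it so that a subject who does *not* agree to keep the routine is excluded.
2. Reconcile exclusion (d) with inclusion (a). The intended rule is for the sponsor to settle. If the item is meant to exclude subjects with a recent IUD insertion or removal, taking out the word *not* achieves that.
3. Carry both corrections into the eligibility form used at screening and at Treatment Visits 1 to 4.

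The cost is one administrative protocol amendment and a form update. Recruitment of the intended population is unaffected.

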2.10 Enrollment

Study candidates who sign the informed consent form, meet eligibility criteria, and undergo initiation of study treatment are considered enrolled. Study treatment initiation is defined as the initiation of treatment with a study device after the placement of the applicator on the intended treatment area on the scheduled treatment day.

2.11 Photo Visit; Required, day -30 to 0

All subjects will have their photos taken within 30 days prior to first study treatment.

- a) Obtain weight.
- b) [REDACTED]
[REDACTED]
[REDACTED]
- c) Obtain baseline 2-Dimensional photographs of the treatment area using standardized setup and settings.

2.12 Study Treatment

[REDACTED]
[REDACTED]
[REDACTED]

[REDACTED] The abdomen and/or buttocks may be treated. [REDACTED]
[REDACTED]
[REDACTED]
[REDACTED]

Treatment Visit 1

Prior to EMS Treatment

- a) Review and confirm subject meets all of the inclusion criteria and none of the exclusion criteria, then proceed with the study treatment.

ZELTIQ P/N: [REDACTED]
Protocol Number: ZA19-002

This document and the contents hereof are considered proprietary and confidential information of ZELTIQ Aesthetics, Inc. Disclosure to unauthorized individuals or dissemination, publication or copying is prohibited without prior written consent of ZELTIQ.

- b) Repeat pregnancy test for female subjects of childbearing potential (urine).
Exclude subject from participation if the results are positive.
- c) Obtain weight (Note: weight measurement is only required prior to first EMS treatment).
- d) Subject completes Body Satisfaction Scale for abdomen and or Body Satisfaction Scale for buttocks as appropriate. Note: Completion of these scales is required prior to first EMS treatment).

EMS Treatment Steps

- e) Apply EMS device per manufacturer's Instructions for Use.
- f) Support the EMS device with pillows or straps as needed.
- g) Initiate treatment using recommended program for toning and firming the targeted treatment area supplied by manufacturer.
- h) Record the highest percent (%) energy utilized for the EMS treatment.

[REDACTED]

[REDACTED]

[REDACTED]

Treatment Visits 2 and 3

The required study activities are the same for both Treatment Visits 2 and 3:

Prior to EMS Treatment

- a) Review and confirm subject meets all of the inclusion criteria and none of the exclusion criteria.
- b) Repeat pregnancy test for female subjects of childbearing potential (urine).
Exclude subject from participation if the results are positive.

EMS Treatment Steps

- c) Apply EMS device per manufacturer's Instructions for Use.
- d) Support the EMS device with pillows or straps as needed.
- e) Initiate treatment using recommended program for toning and firming the targeted treatment area supplied by manufacturer.
- f) Record the highest percent (%) energy utilized for the EMS treatment.

g) [REDACTED]
[REDACTED]
[REDACTED]

Treatment Visit 4

Prior to EMS Treatment

- a) Review and confirm subject meets all of the inclusion criteria and none of the exclusion criteria, then proceed with the study treatment.
- b) Repeat pregnancy test for female subjects of childbearing potential (urine). Exclude subject from participation if the results are positive.

EMS Treatment Steps

- c) Apply EMS device per manufacturer's Instructions for Use.
- d) Support the EMS device with pillows or straps as needed.
- e) Initiate treatment using recommended program for toning and firming the targeted treatment area supplied by manufacturer.
- f) Record the highest percent (%) energy utilized for the EMS treatment.
- g) [REDACTED]
[REDACTED]
[REDACTED]

Post-EMS Treatment # 4

- h) Subject completes Body Satisfaction Scale(s) (for abdomen and/or buttocks, as appropriate)
- i) [REDACTED]
[REDACTED]
- j) Optional - Obtain 2-Dimensional photographs of the treatment area using standardized setup and settings.

The need for post-treatment care is not expected following the EMS treatments performed in this study. Subjects will be encouraged to call the study site if they experience any unusual effects (e.g., severe discomfort etc.), which may be related to the study.

